5.8 Software Version

All analyses will be performed using SAS® software Version 9.4 or higher.

6 STATISTICAL CONSIDERATIONS

6.1 Adjustments for Covariates

Baseline value for the absolute change from baseline of continuous efficacy parameters will be included as covariate in the statistical models.

6.2 Handling of Dropouts or Missing data

See Appendix 2 for handling of completely or partially missing dates for prior and concomitant medications and adverse events.

For safety analyses, no imputation of the data will be done and analyses will be conducted on the observed cases (OC). All efficacy analyses will be performed using Mixed Model Repeated Measures (MMRM) analyses as primary analyses to take care of missing observations. (See section 12.1).

For subjects starting prohibited medications as listed in section 6.4.2 of the protocol, all efficacy data captured after the start of prohibited medication will be considered missing for the analysis

	STATISTICAL ANALYSIS PLAN, Version Final 2.0
Protocol Number: ASN002AD-201 V3.0	Sponsor: Asana BioSciences, LLC

of those parameters. A sensitivity analysis on the primary endpoint EASI will be done including all efficacy EASI data for these subjects (before and after the prohibited medication).

6.3 Interim Analysis and Data Monitoring

No interim analysis is planned for this study. However, unblinded safety data will be generated and reviewed by the DSMB during the study.

The final analyses on efficacy parameters will be done once all patients have finalized their week 12's assessment. All data will be cleaned up to week 12, a soft lock will be performed and final efficacy results will be provided. The efficacy summaries will be updated once the follow-up visit week 16 will be completed, but this will not affect or change any of the final efficacy results.

6.4 Multicenter Studies

To obtain a sufficient and better-balanced number of subjects among study sites, pooling of sites within each country will be applied. Sites without at least 10 subjects in the mITT population will be incorporated into pooled sites as described below. German sites will be pooled together, USA sites will be pooled together and Canadian sites will be pooled together.

Sites in USA or Canada (for each country separately):

- 1) Sites with less than 10 subjects in the mITT will be pooled within a country:
 - a. Sites with less than 10 subjects will be ordered from lowest to highest in terms of number of mITT subjects. In case of ties, the ordering for tied sites will be determined according to the site identification number (from smallest to largest).
 - b. Sites will be combined beginning at the smallest until the resulting pooled site contains at least 10 mITT subjects. The sites pooled in this way will be considered as a single site in the statistical analyses.
 - c. The process described above will resume for the remaining sites not meeting the criterion of at least 10 mITT subjects. If the final set of pooled sites does not meet the criterion of at least 10 mITT subjects, the final set will be pooled with the preceding pooled site.
 - d. If there is only one site with less than 10 mITT subjects, then this site will be combined with the site with the second lowest number of subjects. As above, in the

	STATISTICAL ANALYSIS PLAN, Version Final 2.0
Protocol Number: ASN002AD-201 V3.0	Sponsor: Asana BioSciences, LLC

case of ties, the ordering for tied sites will be determined according to the site identification number (from smallest to largest).

In the case where less than 10 mITT subjects are available in one country, the subjects from both countries will be pooled.

Sites in Germany

- 1) Sites with less than 10 subjects will be ordered from lowest to highest in terms of number of mITT subjects. In case of ties, the ordering for tied sites will be determined according to the site identification number (from smallest to largest).
- 2) Sites will be combined beginning at the smallest until the resulting pooled site contains at least 10 mITT subjects. The sites pooled in this way will be considered as a single site in the statistical analyses.
- 3) The process described above will resume for the remaining sites not meeting the criterion of at least 10 mITT subjects. If the final set of pooled sites does not meet the criterion of at least 10 mITT subjects, the final set will be pooled with the preceding pooled site.
- 4) If there is only one site with less than 10 mITT subjects, then this site will be combined with the site with the second lowest number of subjects. As above, in the case of ties, the ordering for tied sites will be determined according to the site identification number (from smallest to largest).

6.5 Multiple Comparisons/Multiplicity

For the primary endpoint of change-from-baseline in EASI at Week 12, a Hochberg adjustment will be performed to test the three comparisons of interest (40mg vs. Placebo, 60mg vs. Placebo and 80mg vs. Placebo).

Under Hochberg procedure, the comparison proceeds stepwise from the largest *p*-value to the smallest *p*-value to compare the *k*th largest *p*-value with $0.05/k$, which is the significance level corresponding to the *k*th largest *p*-value. The first time a *p*-value is less than the corresponding significance level, the testing stops and the significance is claimed for the current comparison and subsequent ones that produce smaller *p*-values than the current one. If all *p*-values are larger than or equal to the corresponding significance level, none of the doses are statistically different from placebo.

	STATISTICAL ANALYSIS PLAN, Version Final 2.0
Protocol Number: ASN002AD-201 V3.0	Sponsor: Asana BioSciences, LLC

No adjustments will be made to account for multiplicity in secondary and exploratory endpoints and multiple assessments through time in the same subjects. P-values presented for these endpoints will be nominal p-values.

6.6 Examination of Subgroups

The effect of EASI score at baseline (disease severity) on the treatment effect will be examined for the change-from-baseline EASI, %change-from-baseline EASI, and % subjects with at least a 50%, 75% and 90% reduction in EASI, % subjects achieving at least a 2-grade reduction from baseline to clear (0) or almost clear (1) in IGA, % subjects achieving at least a 2-grade reduction from baseline in IGA.

The change and percent change from baseline in single daily timepoint pruritus NRS at Week 1 (Day 2 up to Day 7) and the change and percent change from baseline in weekly average of the peak daily pruritus NRS at Weeks 1, 2, 4, 8, and 12 as well as the % subjects achieving at least a 4-point reduction from baseline in weekly average of the peak daily pruritus NRS at Weeks 1, 2, 4, 8, and 12 will be presented in the subgroup of subjects with baseline NRS ≥ 4 .

Moreover, inferential statistical analysis will be done at Week 12 for change-from-baseline and %change-from-baseline EASI. Details on the inferential statistical analysis are presented under section 12.1 Primary Efficacy Endpoint.

7 STUDY SUBJECTS

7.1 Disposition of Subjects

All subjects who provide informed consent will be accounted for in this study. The number of subjects screened and subjects rescreened will be presented. Screen failures will be presented for all screened subjects except for those who were rescreened and did not fail the second screening. Moreover, the number of subjects randomized included in each population will be presented. Study completion status and the reason for study discontinuation will also be presented. Number of subjects using therapy on study up to Week 12 and the number of subjects continuing into the open label extension are also presented. Percentages will be calculated using the number of subjects randomized as denominator. Number of days in the study will be calculated as follows and will be summarized:

$$\text{Number of days in study} = \text{Date of completion/discontinuation} - \text{1}^{\text{st}} \text{ dose date} + 1$$

A listing of subject's disposition will be provided. Information on first screening for subjects who were rescreened, including the rescreened subject identifier, will be presented under the first

	STATISTICAL ANALYSIS PLAN, Version Final 2.0
Protocol Number: ASN002AD-201 V3.0	Sponsor: Asana BioSciences, LLC

screening subject identifier. A listing of subject's randomization information and a listing of subjects included in each of the study populations will also be provided.

7.2 Protocol Deviations

The number of events and the number and percentage of subjects with at least one major protocol deviation will be summarized by deviation category and treatment group using the safety population. A listing of all major protocol deviations will also be provided.

8 DEMOGRAPHIC AND OTHER BASELINE CHARACTERISTICS

Demographics and baseline characteristics will be summarized with descriptive statistics using the safety population. The list of demographics and baseline characteristics to be summarized will include:

- Age (years) – calculated relative to date of consent
- Age (< 65 years, \geq 65 years) – calculated relative to date of consent
- Self-Reported Gender
- Ethnicity
- Race
- Baseline Height (cm)
- Baseline Weight (kg)
- Baseline BMI (kg/m^2)
- Baseline BSA (%)
- Baseline EASI total score
- Baseline IGA
- Baseline pruritus NRS
- Baseline SCORAD
- Baseline DLQI

	STATISTICAL ANALYSIS PLAN, Version Final 2.0
Protocol Number: ASN002AD-201 V3.0	Sponsor: Asana BioSciences, LLC

- Baseline POEM

A listing of all demographics and baseline characteristics will be provided.

9 SURGICAL AND MEDICAL HISTORY

Medical and surgical history will be coded according to the Medical Dictionary for Regulatory Activities (MedDRA), Version 21.0

Surgical and medical history will be summarized by system organ class (SOC) and preferred term (PT) using the safety population. A subject who experienced the same surgical and medical history event multiple times will be counted only once for the corresponding PT. Similarly, if a subject experienced multiple surgical and medical history events within the same SOC, the subject will be counted only once for that SOC. Surgical and medical history events will be sorted alphabetically by SOC and within each SOC the PT will be presented by decreasing order.

A listing of all surgical and medical history events will be provided.

10 PRIOR AND CONCOMITANT MEDICATIONS

Medications will be coded according to the World Health Organization Drug Dictionary (WHO-DD), March 2018 B2.

Prior medications are defined as any medication started and discontinued prior to the first study treatment dose. Concomitant medications are defined as any medication taken after the first study treatment dose or taken prior to the first study treatment date and continued past that date. See Appendix 2 for handling of completely or partially missing dates for prior and concomitant medications.

Incidence of prior and concomitant medications will be tabulated by Anatomical Therapeutic Chemical Classification System, (ATC) level 2 and PT using the safety population. A subject with the same medication taken multiple times will be counted only once for the corresponding PT. Similarly, if a subject has taken more than one medication within the same ATC level, then the subject will be counted only once for that ATC.

A listing of all prior and concomitant medications will be provided.

	STATISTICAL ANALYSIS PLAN, Version Final 2.0
Protocol Number: ASN002AD-201 V3.0	Sponsor: Asana BioSciences, LLC

11 STUDY TREATMENT EXPOSURE AND TREATMENT COMPLIANCE

A summary of exposure will be presented using the safety population for each treatment group and will include descriptive statistics of the number of days treated for each treatment group. For each treatment, compliance will be calculated as follow:

$$\frac{\text{Number of dose taken}}{\text{Number of days between the last dose date and the first dose date} + 1} \times 100$$

Descriptive statistics for the compliance will be presented for each treatment group. Frequency distribution will also be presented for the following categories: < 80%, [80% - 120%] and > 120%.

Exposure and compliance will be displayed in a listing of study treatment administration.

12 EFFICACY ANALYSIS

12.1 Primary Efficacy Endpoint

The EASI total score for four anatomic sites—head, upper extremities, trunk, and lower extremities—are assessed for erythema, induration/infiltration (papules), excoriation, and lichenification as seen on the day of the examination. The severity of each sign is assessed using a 4-point scale (half steps are allowed):

- 0 = none
- 1 = mild
- 2 = moderate
- 3 = severe

The area affected by atopic dermatitis within a given anatomic site is estimated as a percentage of the total area of that anatomic site and assigned a numerical value according to the degree of atopic dermatitis involvement as follows:

- 0 = no involvement
- 1 = <10%

	STATISTICAL ANALYSIS PLAN, Version Final 2.0
Protocol Number: ASN002AD-201 V3.0	Sponsor: Asana BioSciences, LLC

- 2 = 10% to <30%
- 3 = 30% to <50%
- 4 = 50% to <70%
- 5 = 70% to <90%
- 6 = 90% to 100%

The EASI score is obtained by using the formula below:

$$\text{EASI} = 0.1 (\text{Eh} + \text{Ih} + \text{Exh} + \text{Lh}) \text{Ah} + 0.2 (\text{Eu} + \text{Iu} + \text{Exu} + \text{Lu}) \text{Au} + 0.3 (\text{Et} + \text{It} + \text{Ext} + \text{Lt}) \text{At} + 0.4 (\text{El} + \text{Il} + \text{Exl} + \text{Ll}) \text{Al}$$

Where E, I, Ex, L, and A denote erythema, induration, excoriation, lichenification and area, respectively, and h, u, t, and l denote head, upper extremities, trunk, and lower extremities, respectively. The score will be set to missing in case of at least one missing value.

Descriptive statistics on EASI total score will be presented by visit for each treatment group. Change from baseline and percentage change from baseline will be also summarized.

Primary Endpoint Analysis

The primary efficacy endpoint is change from baseline in EASI score at Week 12. The primary efficacy analysis will be done using the mITT population and the PP population will be used as a supportive analysis.

A mixed effect model for repeated measures (MMRM) will be used to model the change from baseline in EASI score between treatments. The model will include treatment, visit, stratification factor (baseline disease severity, [EASI = 16.0-21.2] vs. [EASI = 21.3-29.9] vs. [EASI = \geq 30.0]), and treatment-by-visit interaction as fixed effects. The unstructured (UN) variance-covariance matrix and Kenward Roger degrees of freedom will be used.

Information for stratification factor will be taken from the Electronic Data Capture (EDC) database, and not the IWRS for primary analysis.

Sensitivity Analyses

An analysis of variance (ANOVA) will be performed, where the absolute change from baseline in EASI score at Week 12 will be the dependent variable, the treatment group and stratification factor (baseline disease severity) will be fixed effects. A supportive analysis with pooled site and pooled

	STATISTICAL ANALYSIS PLAN, Version Final 2.0
Protocol Number: ASN002AD-201 V3.0	Sponsor: Asana BioSciences, LLC

site-by-treatment interaction included as fixed factors in addition to the other factors listed above will be performed in order to study the impact of pooled site on efficacy. If the pooled site-by-treatment interaction is not statistically significant, it will be removed from the model.

An additional sensitivity analysis will be carried out on the change from baseline in EASI score at Week 12 where data from site 029 is excluded.

Distribution of residuals will be visually examined to determine whether substantial departures from normality and homogeneity of variance are apparent. If the data are inconsistent with the assumption of normality, a nonparametric analysis of variance will be performed.

Additional sensitivity analyses will be performed using the stratification factor as per IWRS database in the primary efficacy MMRM model described above and including all efficacy EASI data for these subjects (before and after the prohibited medication).

	STATISTICAL ANALYSIS PLAN, Version Final 2.0
Protocol Number: ASN002AD-201 V3.0	Sponsor: Asana BioSciences, LLC

Subgroup Analyses

An analysis of variance (ANOVA) will be performed, where the absolute change from baseline or the percent change from baseline in EASI score at Week 12 will be the dependent variable, the treatment group and stratification factor as per EDC (baseline disease severity, [EASI = 16.0-21.2] vs. [EASI = 21.3-29.9] vs. [EASI = \geq 30.0] and treatment-by-stratification factor will be fixed effects. Treatment effect per stratification factor subgroup will be presented as well as associated p-values.

12.2 Secondary Endpoints

Eczema Area and Severity Index (EASI):

EASI score (as a secondary endpoint) will be assessed as:

- Change from baseline in EASI score at Weeks 2, 4, and 8
- Percent change from baseline in EASI score at Weeks 2, 4, 8, and 12
- Proportion of subjects with at least a 50% reduction from baseline in EASI (EASI50) at Weeks 2, 4, 8, and 12.
- Proportion of subjects with at least a 75% reduction from baseline in EASI (EASI75) at Weeks 2, 4, 8, and 12.
- Proportion of subjects with at least a 90% reduction from baseline in EASI (EASI90) at Weeks 2, 4, 8, and 12.
- Time to EASI50, EASI75 and EASI90 relative to baseline.

Investigator Global Assessment (IGA):

The Investigator Global Assessment (IGA) is a site-administered clinician-reported global assessment of the current state of the disease. It is measured on a 5-grade scale from 0 to 4, where 0 = clear to 4 = severe.

IGA will be assessed as

- Proportion of subjects achieving at least a 2-grade reduction from baseline to clear (0) or almost clear (1) in IGA at Weeks 2, 4, 8, and 12.
- Proportion of subjects achieving at least a 2-grade reduction from baseline in IGA at Weeks 2, 4, 8, and 12.

	STATISTICAL ANALYSIS PLAN, Version Final 2.0
Protocol Number: ASN002AD-201 V3.0	Sponsor: Asana BioSciences, LLC

Body Surface Area (BSA):

The overall body surface area (BSA) affected by atopic dermatitis is evaluated (from 0% to 100%).

BSA will be assessed as

- the change and percent change from baseline in BSA involved with AD at Weeks 2, 4, 8, and 12.

SCORing Atopic Dermatitis (SCORAD):

The Scoring Atopic Dermatitis (SCORAD) is built from six items (erythema, edema/papulation, oozing/crusts, excoriation, lichenification, and dryness) selected to evaluate the atopic dermatitis severity. The intensity of each item is graded using a 4-point scale (half steps not allowed)

- 0 = absence
- 1 = mild
- 2 = moderate
- 3 = severe

The area chosen for grading must be representative (average intensity) for each item. The individual intensity ratings for each item will then be added (ranging from 0-18) and multiplied by 3.5, giving a maximal score of 63.

The overall BSA affected by atopic dermatitis is evaluated (from 0% to 100%) and divided by 5. One subject's palm represents 1% of his or her total BSA. The maximum is 20.

Subjective items include loss of sleep and the intensity of pruritus. These are evaluated by having the subjects indicate on a 10.0-cm (0.0 – 10.0) visual analog scale (VAS) the point corresponding to the average value for the last 3 days/nights. The combined maximum score of these two is 20.0.

The sum of the measures above represents the SCORAD, which can vary from 0 to 103. If the subjective scores of pruritus and loss of sleep are excluded, the SCORAD becomes objective SCORAD (score range 0.0-83.0). The score will be set to missing in case of at least one missing value.

SCORAD will be assessed as

[figure not shown]
	STATISTICAL ANALYSIS PLAN, Version Final 2.0
Protocol Number: ASN002AD-201 V3.0	Sponsor: Asana BioSciences, LLC

- the change from baseline in total SCORAD score, sleep and pruritus sub-scores at Weeks 2, 4, 8, and 12.
- The percent change from baseline in total SCORAD score, sleep and pruritus sub-scores at Weeks 2, 4, 8, and 12.

Pruritus Numeric Rating Scale (NRS):

The intensity of pruritus will be recorded for the entire duration of the treatment (daily) using a numeric rating scale (NRS). This will be evaluated by asking subjects to assign a numerical score representing the worst intensity over the last 24 hours of their symptoms on a scale from 0 to 10, with 0 indicating no symptoms and 10 indicating the worst imaginable symptoms. The pruritus NRS is presented in Figure 2. Assessments within 7 days prior to each of the Week 2, 4, 8, and 12 visits, and on Days 2 to 7 of the Week 1 visit, will be used for the calculation of the weekly average of pruritus NRS.

Figure 2: Pruritus Numeric Rating Scale

The pruritus numeric rating scale will be assessed as:

- Change and percent change from baseline in single daily timepoint NRS at Week 1 (i.e. Day 2, Day 3, up to Day 7).
- Change and percent change from baseline in weekly average of the peak daily pruritus NRS at Weeks 1, 2, 4, 8, and 12.
- Proportion of subjects achieving at least a 4-point reduction from baseline in weekly average of the peak daily pruritus NRS at Weeks 1, 2, 4, 8, and 12.

	STATISTICAL ANALYSIS PLAN, Version Final 2.0
Protocol Number: ASN002AD-201 V3.0	Sponsor: Asana BioSciences, LLC

- Time to a 4-point reduction from baseline in weekly average of the peak daily pruritus NRS.

5D-Pruritus Scale:

The 5-D Pruritus Scale is a 1-page, 5-question, validated questionnaire used in clinical trials to assess 5 dimensions of background itch: degree, duration, direction, disability, and distribution. Each question corresponds to 1 of the 5 dimensions of itch; subjects will rate their symptoms over the preceding 2-week period as “present” or on a 1 to 5 scale, with 5 being the most affected.

The scores of each of the five domains are achieved separately and then summed together to obtain a total 5-D score. 5-D scores can potentially range between 5 (no pruritus) and 25 (most severe pruritus). The score will be set to missing in case where at least one of the five domain results is missing. Single-item domain scores (duration, degree and direction) are equal to the value in the response choice (range 1–5). The disability domain includes four items that assess the impact of itching on daily activities: sleep, leisure/social activities, housework/errands and work/school. The score for the disability domain is achieved by taking the highest score on any of the four items. For the distribution domain, the number of affected body parts is tallied (potential sum 0–16) and the sum is sorted into five scoring bins: sum of 0–2 = score of 1, sum of 3–5 = score of 2, sum of 6–10 = score of 3, sum of 11–13 = score of 4, and sum of 14–16 = score of 5.

The 5D-Pruritus Scale will be assessed as

- the change from baseline in 5-D Pruritus Scale at Weeks 2, 4, 8, and 12.

Patient-Oriented Eczema Measure (POEM):

The Patient-Oriented Eczema Measure (POEM) is a self-assessment of disease severity by the subject. The POEM has a maximum value of 28 based on the subject’s response to seven questions scored from 0 to 4. The score will be set to missing in case of at least one missing value.

POEM will be assessed as

- the change from baseline in POEM at Weeks 2, 4, 8, and 12.

Dermatology Life Quality Index Questionnaire (DLQI):

Dermatology Life Quality Index Questionnaire (DLQI) is a simple 10-question validated questionnaire that has been used in more than 40 different skin conditions. The DLQI is the most frequently used

	STATISTICAL ANALYSIS PLAN, Version Final 2.0
Protocol Number: ASN002AD-201 V3.0	Sponsor: Asana BioSciences, LLC

instrument in studies of randomized controlled trials in dermatology. The DLQI total score is defined as the sum of the 10 item scales, ranging from 0 to 30. If missing answers or mistakes, the following rules will be followed:

1. If one question is left unanswered this is scored 0 and the scores are summed and expressed as usual out of a maximum of 30.
2. If two or more questions are left unanswered the questionnaire is not scored.
3. If question 7 is answered 'yes' this is scored 3 even if in the same question one of the other boxes is ticked.
4. If question 7 is answered 'no' or 'not relevant' but then either 'a lot' or 'a little' is ticked this is then scored 2 or 1. If it is answered 'no', but the second half is left incomplete, the score will remain 0.

DLQI will be assessed as

- the change from baseline in DLQI at Weeks 2, 4, 8, and 12.

Secondary Endpoint Analyses

The same methods (MMRM and ANOVA) as described for the primary efficacy analyses (Section 12.1) will be performed to analyze the change and percent change in EASI.

Similar methods (MMRM and ANCOVA) as described for the primary efficacy analyses (Section 12.1) will be performed to analyze the change and percent change in NRS, SCORAD (MMRM and ANCOVA for total score; MMRM only for sleep and pruritus sub-scores) and BSA, and the change in 5D-Pruritus Scale (change from baseline only), POEM (change from baseline only) and DLQI (change from baseline only), with the addition of the baseline score as covariate in the models. Analyses will be based on the mITT population for all secondary parameters.

For categorical efficacy endpoints involving proportions of IGA, EASI and NRS (e.g. the proportion of subjects achieving at least a 2-grade reduction from baseline to clear (0) or almost clear (1) in Investigator's Global Assessment (IGA) at week 12), a Cochran Mantel Hansel test (CMH) controlling for the stratification variable (baseline disease severity) will be performed. For subgroup analyses at each level of baseline severity, a Chi-squared test will be performed. Analyses will be based on the mITT population for all secondary parameters and also on PP population for IGA.

	STATISTICAL ANALYSIS PLAN, Version Final 2.0
Protocol Number: ASN002AD-201 V3.0	Sponsor: Asana BioSciences, LLC

As a sensitivity analysis for IGA, the Cochran Mantel Hansel test (CMH) controlling for the stratification variable (baseline disease severity) will be performed, excluding the subjects for whom the IGA form was initially used to capture the vIGA assessment at baseline. This sensitivity analysis will be performed on the mITT and PP populations.

Additional exploratory analyses may be performed to further understand the impact, if the results of the sensitivity analyses excluding the subjects for whom the IGA form was initially used to capture the vIGA assessment at baseline reveal inconsistencies with the results including those subjects.

The time to achieve the 50%, 75%, or 90% reduction in EASI relative to baseline and the time to achieve a 4-point reduction from baseline in weekly average of the peak daily pruritus NRS will be compared between treatments using the Kaplan Meier method. A subject will be considered as censored if he has not met the event of interest at the end of the study (Week 12 visit) or if the subject is lost to follow up at last observation. Those subjects will be censored at their last available EASI (or NRS) assessment.

Information for stratification factors will be taken from the EDC database, and not the IWRS for all secondary endpoint analyses.

Descriptive statistics will be presented on all secondary endpoints by visit and treatment group.

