### 3 OBJECTIVES AND ENDPOINTS

OBJECTIVES	ENDPOINTS
Primary  To evaluate the efficacy of ASN002 in subjects with moderate to severe AD	
Primary efficacy endpoint:
 

• Change from baseline in EASI score at Week 12

 
Secondary efficacy endpoints:
 

• Change from baseline in EASI score at Weeks 2, 4, and 8

• Percent change from baseline in EASI score at Weeks 2, 4, 8, and 12

• Proportion of subjects with at least a 50% reduction from baseline in EASI (EASI50) at Weeks 2, 4, 8, and 12

• Proportion of subjects achieving at least a 75% reduction from baseline in EASI (EASI75) at Weeks 2, 4, 8, and 12

• Proportion of subjects achieving at least a 90% reduction from baseline in EASI (EASI90) at Weeks 2, 4, 8, and 12

• Time to achieve EASI50, EASI75, and EASI90 relative to baseline.

• Proportion of subjects achieving at least a 2-grade reduction from baseline to clear (0) or almost clear (1) in IGA at Weeks 2, 4, 8, and 12

• Proportion of subjects achieving at least a 2-grade reduction from baseline in IGA at Weeks 2, 4, 8, and 12

• Proportion of subjects achieving an IGA of clear (0) or almost clear (1) at Weeks 2, 4, 8, and 12

• Change from baseline in SCORAD at Weeks 2, 4, 8, and 12

• Change from baseline in 5-D Pruritus Scale at Weeks 2, 4, 8, and 12

• Change and percent change from baseline in single daily timepoint pruritus NRS at Week 1

• Change and percent change from baseline in weekly average of the peak daily pruritus NRS at Weeks 1, 2, 4, 8, and 12

• Proportion of subjects achieving at least a 4-point reduction from baseline in weekly average of the peak daily pruritus NRS at Weeks 1, 2, 4, 8, and 12

• Change and percent change from baseline in BSA involved with AD at Weeks 2, 4, 8, and 12

• Change from baseline in POEM at Weeks 2, 4, 8, and 12

• Change from baseline in DLQI at Weeks 2, 4, 8, and 12

Secondary  To evaluate the safety and tolerability of ASN002 in subjects with moderate to severe AD	
Secondary safety endpoints:
 

• Number of TEAEs

OBJECTIVES	ENDPOINTS

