5.5 Descriptive Statistics

All continuous variables will be summarized by presenting the number of subjects, mean, standard deviation, median, minimum, and maximum. Categorical variables will be presented as frequencies and percentages. Summary tables will be presented by treatment and visit, when applicable.

Change from baseline will be calculated as:

Assessment value at post-baseline visit X – baseline value.

Percent change from baseline will be calculated as:

(Assessment value at post-baseline visit X – baseline value) / baseline value * 100.

	STATISTICAL ANALYSIS PLAN, Version Final 2.0
Protocol Number: ASN002AD-201 V3.0	Sponsor: Asana BioSciences, LLC

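### Percent change in the SCORAD sleep and pruritus sub-scores divides by a baseline that can be 0, so the mean could rest on a few subjects and disagree with the absolute change

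*SAP*

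**What the plan says.** **Endpoint.** Protocol section 3 asks for "Change from baseline in SCORAD at Weeks 2, 4, 8, and 12". SAP section 2 and SAP 12.2 add percent change and the two patient-reported components: "The percent change from baseline in total SCORAD score, sleep and pruritus sub-scores at Weeks 2, 4, 8, and 12".

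**Formula.** SAP 5.5 introduces it with "Percent change from baseline will be calculated as" and gives 100 x (post-baseline value - baseline) / baseline. There is no rule for a zero or very small baseline.

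**Scale.** SAP 12.2 scores sleep loss and pruritus each on a 10 cm visual analogue scale from 0.0 to 10.0.

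**Model.** The Secondary Endpoint Analyses part of SAP 12.2 specifies "MMRM only for sleep and pruritus sub-scores", for change and percent change, with the baseline score as covariate, in the mITT population.

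**Entry criteria.** Protocol 5.1 requires EASI of at least 16, IGA of at least 3 and BSA of at least 10%. Neither 5.1 nor 5.2 sets a minimum itch or sleep-loss score. In Appendix A, pruritus is one of four major criteria, of which three suffice. Sleep loss is not a criterion.

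**NRS, for comparison.** It is scored "on a scale from 0 to 10, with 0 indicating no symptoms", and its endpoints include "Change and percent change from baseline in weekly average of the peak daily pruritus NRS at Weeks 1, 2, 4, 8, and 12". The protocol also lists percent change for NRS. SAP 6.6 adds a presentation in subjects with baseline NRS of at least 4. The sub-scores have no counterpart.

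**The concern.** For EASI and BSA the entry criteria guarantee a usable denominator. They also keep total SCORAD away from 0, so that part of the endpoint is not in question. Nothing protects the two sub-scores, and sleep loss is the more exposed, because a subject can have moderate to severe disease and sleep well.

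Two things follow if some subjects enter at or near 0:

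- Subjects at exactly 0.0 are removed from the percent-change analysis at every visit, although they could only stay the same or worsen.
- Subjects just above 0 can have very large positive values, which nothing on the other side can offset, since improvement stops at -100%. A model for means gives these values full weight.

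The report could then carry two results for the same scale that disagree: a clear benefit on absolute change and little or none on percent change.

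**Working it through.** **The plan's own figures.** The plan states no figure for any percent-change endpoint. The 46 per arm used below is the minimum evaluable number in SAP 5.1. It is consistent with the rest of that section: 46 per group with 37.5% versus 11.1% gives 80.0% power by Fisher's exact test (stated: 80%), and 46 / 0.85 = 54.1, rounded up to 55.

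**Step 1: single subjects.** The SAP 5.5 formula gives the percent change, and dividing by 46 gives that subject's contribution to an arm mean.

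| Baseline to follow-up | Percent change | Contribution to arm mean |
|---|---|---|
| 0.0 to any value | undefined | none |
| 0.1 to 3.0 | +2,900% | +63.0 points |
| 0.2 to 2.0 | (2.0 - 0.2) / 0.2 = +900% | +19.6 points |
| 0.5 to 3.0 | +500% | +10.9 points |
| 6.0 to 3.0 | -50% | -1.1 points |

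The 0.1 to 3.0 subject outweighs 46 subjects who each improve by 50% (46 x 50 = 2,300 points).

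**Step 2: subjects lost.** Assumed zero-baseline rates of 1%, 2% and 5% remove 220 x 0.01 = 2.2, 220 x 0.02 = 4.4 and 220 x 0.05 = 11 subjects.

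**Step 3: effect on the comparison.** Assumptions, none of them from the documents:

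- Baseline is 10 x Beta(a, b), with a share set to zero.
- Follow-up is baseline x (1 - d) plus normal noise with SD 2.0, truncated to 0-10, with d = 0.25 on placebo and 0.55 on active.
- 46 per arm, two-sided unadjusted t-test at 5% on one visit, zero baselines dropped from percent change.

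| Assumed baseline | Power, absolute change | Power, percent change |
|---|---|---|
| Beta(4, 2.5), few low values | 98% | 96% |
| Beta(2, 2), 5% at zero | 83% | 57% |
| Beta(1.1, 1.3), nearly flat, 5% at zero | 74% | 23% |

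Separate runs of the same model differ by a point or two; one run of the first row gave 94% for percent change. In the nearly flat case the estimated difference in mean percent change favours placebo in 19% of simulated trials.

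**Step 4: does the planned baseline covariate help?** Analysis of covariance gives 90% (absolute) versus 23% (percent) in the nearly flat case and 92% versus 59% for Beta(2, 2). It raises power for absolute change and does little for percent change.

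**Step 5: a second set of assumptions.** Typical baselines have mean 6.5 and SD 2, with mean falls of 3 (active) and 1 (placebo). A small share of subjects enters at 0 or between 0.1 and 1 and has a follow-up mean of about 2 in either arm.

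| Share at 0 / near 0 | Absolute | Percent | Percent, rank test |
|---|---|---|---|
| 0% / 0% | 99.7% | 99% | 99% |
| 1% / 1% | 99% | 79% | 99% |
| 2% / 3% | 98% | 50% | 98% |
| 5% / 5% | 95% | 30% | 96% |

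**Step 6: a floor.** Restricting to baseline of at least 4 restores power on percent change to 98% in the last row of Step 5 and to about 85% in the nearly flat case of Step 3.

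**Step 7: NRS.** Taking whole-number baselines, the smallest non-zero value is 1, so the largest possible value is (10 - 1) / 1 = +900%. In the Step 5 setting, power on percent change is 99%, 94%, 82% and 69%: the same pattern, less pronounced.

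**The case against.** **The harm is conditional.** A reader might infer that values will be undefined and that near-zero baselines will dominate. The documents do not support that: they give no baseline distribution for sleep loss or itch. With few low baselines, percent change loses almost nothing. This objection stands, and the point is worded as a risk against which the plan has no protection.

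**NRS is not the same case.** A reader might extend the point equally to NRS. Percent change in NRS is in the protocol, the coarser scale limits the extremes, and SAP 6.6 already presents it for baseline NRS of at least 4. This stands as well. What remains is that the mITT percent-change analysis of NRS is kept beside that presentation with no stated precedence.

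**The valid analysis is already there.** Absolute change with baseline as covariate is planned for both sub-scores and keeps subjects at 0. SAP 5.5 and 12.2 also provide medians, minima and maxima by visit and treatment, so a mean driven by outliers could be seen. This limits the consequence. It is also why removing the percent-change inference costs little.

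**The nonparametric fallback.** SAP 12.1 allows a nonparametric analysis if normality fails. It is written for the primary EASI analysis, and the sub-scores are assigned MMRM only. Even if extended, a rank method would limit the influence of extreme values but could not supply a value for a zero baseline.

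**An unlisted change.** A reader might treat the absence of these additions from SAP 3.5 as evidence for the concern. SAP section 2 lists them openly, so this is a separate documentation gap and does not bear on the denominator.

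**Conclusion.** The point holds for the SCORAD sleep and pruritus sub-scores. As written, the plan drops any subject with baseline 0.0 from the percent-change analysis and lets near-zero baselines enter a mean-based model without a floor. The mean percent change could therefore be driven by a few subjects and could disagree with the absolute change.

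The size is not known. Under the assumed effects and noise with 46 per arm, power on absolute versus percent change runs from about 98% versus 96% to 74% versus 23%, depending on how many subjects enter low. These figures come from single-visit tests, not the full MMRM. The covariance-adjusted check shows that the planned baseline covariate does not remove the problem.

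Importance is minor. SAP 6.5 makes secondary p-values nominal, absolute change is analysed alongside, and the primary endpoint is untouched. For NRS only a lesser version applies.

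**What to change.** In SAP 12.2, do one of the following for the sleep and pruritus sub-scores:

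1. Drop the inferential percent-change analysis and rely on the absolute change with baseline as covariate, which is already planned and keeps every subject with data. This is the simpler choice.
2. Keep percent change, but only in subjects with a sub-score baseline of at least 4, mirroring the NRS threshold in SAP 6.6. This also settles the zero-baseline case.

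For NRS, state that the baseline NRS of at least 4 analysis is the percent-change result of record and show the mITT percent change descriptively only. Because the protocol lists NRS percent change, record this in SAP 3.5.

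The cost is SAP wording. One inferential display that the SAP added is lost or limited to a subset, and under option 2 the result no longer describes subjects with mild symptoms at entry. No data collection or primary analysis changes.
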